- Ethnicity: Hispanic
- Insurance: Medicaid or uninsured

We conducted a feasibility assessment of possible Nemours patients meeting the same criteria, albeit with a de-identified database, and found that there were 212 potential participants meeting the above criteria.

We will send the flyer entitled "Recruitment of a Diverse Parent Crowd" to all parents of Nemours patients in the database via email (if available) or regular mail (if email is not available). Our study email address ([contact]) and PI's phone number are provided on the flyer. Parents are instructed to contact the research team to sign up for the focus group. As mentioned, we will recruit up to 20 parents from the database. If 20 parents do not contact us and consent to participation within two weeks of distribution of the flyer, then our research coordinator will telephone parents to invite them to participate. We will be conducting the focus group across three Nemours sites (Orlando, Jacksonville, Delaware) via videoconference. The date/time of the focus group will be determined pending IRB approval, but will likely take place in the evening to accommodate work schedules. Each site will have 1-2 trained focus group facilitators who are all existing members of the research team. We have already asked our existing Parent Crowd 16 questions regarding parental burden and emotions, impact on the young child with T1D and other family members, and health care

interactions, and we have integrated the responses into a social-ecological framework which will drive the content of the online resource. The purpose of this focus group will be to obtain these parents' perspectives of raising a very young child with T1D by asking similar questions to assure that our website content is generalizable across demographic groups. The 16 questions posed to the Parent Crowd have been condensed into 6 questions (below) which will be asked by the focus group facilitator to prompt discussion. Parents will also be asked to complete a demographic form prior to the start of the focus group. At the end of the focus group, parents will be invited to join the Parent Crowd and continue to participate in the design and development of the online resource. Participants will be paid \$25 for their time and effort on a CT payer card which we are already using to pay Parent Crowd participants for their responses to questions.

We request a waiver of the requirement for documentation of *full* informed consent for focus group participation. We completed a waiver for documentation of informed consent, as participants will read and sign an abbreviated consent form (attached). Given that there is minimal risk of participation in this focus group we did not think the full consent process was necessary. Parents will be provided the abbreviated consent form prior to beginning the focus group and completing the demographic form. The consent form document will be read to them by the focus group facilitator. They will be encouraged to ask questions about participation in the focus group prior to signing the consent form. Once signed, they will be given a copy of the form which provides all necessary information about the study procedures, risks, and confidentiality. As mentioned, at the end of the focus group, parents will be invited to join the Parent Crowd. Given that all parents provided electronic consent to participate in the Parent Crowd (Website Design and Development Phase), all focus group participants will be required to provide the same electronic consent. Thus, an abbreviated consent is being requested only for focus group participation.

HCP Crowd Input: The Family Advisors will decide which Parent Crowd decisions will be reviewed by the HCP Crowds via the Nemours VAC platform. Serving in an advisory capacity, HCPs will review the proposed design elements, identify additional areas for consideration, and indicate whether all proposed content is consistent with existing scientific evidence. Content areas will be further refined in accord with their recommendations. If any new or different information is proposed, parents will be asked to evaluate this information again.

Application Developer Input: Once the initial ideas for website content, structure and function are approved by parents, HCPs, and the research team (including the Family Advisors), draft specifications will be reviewed with the web development agency, who will develop a roadmap of design challenges to be distributed to their expert application developers in building the resource. [name] of Nemours web development team will be continuously involved throughout the design process to ensure that the website platform can be readily integrated into the Nemours.org public website. As elements of the website become available from the web development agency, parent and HCP stakeholders will review each element again. If parents identify any problems with the element, they will be asked to provide further input. This will be reviewed again by HCPs who will function in an advisory capacity. This cyclical process will continue for all elements until there is a final product that is acceptable to all stakeholders (see Figure 2).

Final Website Design: Once parents, HCPs, and the researchers approve the completed portal, the Nemours Web Development Team will incorporate the final platform into a functioning online resource on a Nemours website, with access limited to participants randomized to Website. The Parent Crowd will determine how HCP input will be integrated into the portal. A last step in constructing the portal will be to populate the compilations of behavior management, emotional coping and daily hassle strategies so that the RCT can begin with some helpful resources in place. The Parent Crowd and Family Advisors will determine if this content will be parent-initiated or HCP-initiated strategies or if a hybrid model of incorporation of ideas will be used. These resources will give step by step instructions, guidelines for determining appropriate uses of each strategy and opportunities for rating of the feasibility and effectiveness of each strategy by parent-users. The website will include a mechanism for expanding these compilations based on user experience over time. Family Advisors will beta test the finished platform and any issues will be resolved before the RCT is opened for enrollment.

4.2. Randomized Controlled Trial (RCT): During Years 3-4, we will conduct an RCT of the website compared with Usual Care (UC) in a sample of up to 300 parents of children with T1D (<6 years old). Details follow:

Participants: The RCT will enroll up to 300 parents of children <6 years old who receive T1D care at any of five Nemours Children's Health System sites in the Delaware Valley and Florida or who are recruited online

using a variety of internet resources from among eligible parents who live elsewhere in the United States. . As noted in Facilities and Resources, Nemours YC-T1D population was recently estimated at 213 patients, with a slightly increasing trend over the past 4 years. We anticipate that about 25% will be ineligible for one or more reasons and that another 10-15% will not be interested in participating in the study. With a 60% recruitment rate, we project that parents of up to 120 Nemours patients will enroll and that we will recruit the remaining parents via the various online methods, all of which are established, publicly available resources of the Diabetes Online Community that are already frequented by parents of this clinical population. Since parents will collect and ship dried blood spot samples from children who do not receive T1D care at Nemours, study participants must reside in the United States due to logistic and cost considerations associated with international shipping of these samples. One parent's participation is required, but two parents of the same child will be encouraged to take part, in which case the mother and father will complete the measures separately. We estimate that 75 fathers will enroll, but we will enroll any/all who wish to do so. Minorities and those with economic or educational disadvantages may have limited access to social media. If necessary to achieve sample composition consisting at least of 28% racial minorities and of 7% Hispanic ethnicity, we will continue selective recruitment of racial and ethnic minorities after concluding recruitment of non-Hispanic Whites in order to oversample from these groups to ensure that our parent sample is very diverse. There is no minimum duration of T1D, nor is there an HbA1c cutoff as the website is intended for all YC-T1D parents.

Inclusion criteria: Parent or legal guardian of a child with physician diagnosis of T1D; Parent age ≥ 18 years; Child with T1D is currently < 6 years old; Parent able to read and comprehend English; Regular access to the internet.

Exclusion criteria: Inability to read/comprehend study questionnaires and decision aids in English; Participating parent or the child with T1D lives outside of the United States.

Recruitment and Informed Consent: The study, including this recruitment plan, will be approved by a Nemours IRB before recruitment begins.. All Nemours health care providers who see T1D patients will receive an e-mail notice describing this study and our plan to contact all potentially eligible parents of Nemours T1D patients about enrollment, All potential Nemours participants that meet enrollment criteria will be identified through Nemours EMR and will receive an emailed study flyer approved by Nemours Marketing and Communications Department,, followed by phone and/or direct contact in the clinic. Online recruitment of the remaining participants will be facilitated by our internet marketing consultant, [name], who will disseminate word of our study and the IRB-approved study flyer using any of several announcements that we have drafted and that have been approved by the Nemours IRB. Internet resources will include Facebook groups such as Diapers and Diabetes and T1D Mod Squad; websites of diabetes organizations such as Children with Diabetes, Children's Diabetes Foundation, and JDRF; and blogs such as Naturally Sweet Sisters. The RCT entails a large group of people using the website together, so we will recruit and enroll all participants over a 1-2 month interval and begin all of them in the trial as close to concurrently as possible. The Nemours IRB has approved our proposal that parental permission and informed consent be obtained electronically since this is adequate participant protection and because it can provide valuable experience to justify this same approach in a future multi-site clinical trial, as we plan.

Study design: The design is a 2X3 randomized treatments design with 2 groups (Website and Usual Care/UC) and 3 measurements (0, 6, and 12 Months). To enable moderation and mediation analyses, randomization will be stratified by site; each site will randomize families to Website and UC in a 2:1 ratio. The primary outcome is change in HbA1c over 6 mos. Usual Care at Nemours is designed to conform to the 2017 ADA *Standards of Medical Care in Diabetes*. All patients will receive the same care offered to patients outside of this study. Those randomized to Website will receive all of the elements of Usual Care, supplemented with access to the online resource for 1 year after randomization.

Optional Supplemental Methods of Communication with Participating Parents: Participants randomized to Website will also be provided with the option to receive website updates (i.e., new articles posted, active parent-to-parent forum discussions) via an emailed newsletter, Facebook, and/or Twitter. All three of these communication tools will serve the same purpose, which is to encourage participants to visit the website by providing updates through resources that many of them already use frequently (i.e., email and social media). The Facebook group (The New Normal T1D) and Twitter handle (@thenewnormalt1d) will set up as "private" and "protected" such that only select people (i.e., website participants) would be able to access the Facebook

group and see tweets. Users will not be able to post on the Facebook page or tweet to us or each other, thus conversations among users (outside of our website) will not be possible. We are working with the Nemours Social Media Manager to set these up to meet the appropriate privacy specifications. Participants will be required to opt in to receiving the newsletter when they register for the website. Participants will also be to opt in to receiving website updates through Facebook and/or Twitter. If they indicate “yes” then they will be added to the Facebook page and/or encouraged to follow @thenewnormalt1d on Twitter, respectively. Parents randomized to UC will be invited to use the website for 6 months following the first 6 months of the randomization phase of the trial. After the trial is completed, every effort will be made to maintain the website indefinitely.

Measurement Strategy: The measurement plan aligns directly with the conceptual model. Little is known about variables that might influence and be influenced by parent use of the planned website, so the measurement plan for this trial is broad in scope. This will magnify participation burden, but the collection of a thorough assessment of model constructs will best facilitate planning a future, larger trial, to evaluate the model in its entirety and to determine if parent or child characteristics moderate or mediate website benefits. Hence, parents will be paid for completing scheduled measures on an escalating basis: Baseline \$25; 6 months: \$50 and 12 months: \$75. Questionnaires will be completed online using existing REDCap capabilities. T1D-specific measures were reviewed by the Family Advisors and adapted for the YC-T1D population. The conceptual model constructs associated with each measure are denoted as follows: Social Support (SS), Individual Parent Characteristics (IPC), Affective Coping (AC), Behavioral Coping (BC), Individual Child Characteristics (ICC), T1D Management Behaviors (DMB), Hypoglycemia (H), Glycated hemoglobin (A1C), and Quality of Life (QOL). Certain measures, as described in the Human Subjects section, yield clinical cutoff scores. Parents or children whose scores on those measures exceed a clinical cutoff will be contacted promptly and assisted in arranging an appointment with a qualified mental health professional in their areas. The Eyberg Child Behavior Inventory and the Brief Symptom Inventory-18 are commercially available. Per communication with the publishers (PAR and Pearson, respectively; see Appendix A), we have received approval pending completion of license/fee agreements to administer these measures online via REDCap.

Measures obtained at Baseline only:

Demographic information (IPC and ICC): The same demographic form used in the Website Design and Development Phase will be collected from RCT participants at baseline.

Perceived spousal support (SS): The Family Management Measure¹⁴⁸ assesses how families manage caring for children with chronic conditions like T1D. We will use the 8-item Parental Mutuality scale that measures parents' perceptions of support, shared views, and satisfaction with how the partners work together to manage the child's condition. The scale will be completed only by parents living with adult partners. The scale has adequate internal consistency ($\alpha=0.73$ for mothers, $\alpha=0.77$ for fathers), inter-rater reliability ($r=0.44$), and test-retest reliability ($r=.71$), and correlations in the expected direction with measures of related constructs.

Eyberg Childhood Behavior Inventory (ECBI) (ICC): The ECBI¹⁶¹ is a widely used parent-report measure of problematic behaviors of children ≥ 2 years old. Parents rate the frequency of 36 child behaviors on a Likert scale, that ranges from 1 (*never*) to 7 (*always*), and to then indicate whether they consider each behavior to be a problem (yes/no). The ECBI has strong reliability and validity.¹⁶² The ECBI will be administered at Baseline only to provide a comparator for evaluation of the convergent validity of the Preschool Diabetes behavior Checklist described below.

Diabetes-specific routines (BC): The Pediatric Diabetes Routines Questionnaire (PDRQ)³⁷ measures the frequency of routines formed around managing diabetes in the family. Item frequency is measured on a 5-point Likert scale ranging from 0 “never” to 4 “everyday” and “not applicable.” Internal consistency ($\alpha=0.88$) and test-retest reliability ($r=0.81$) estimates were strong. Construct validity was supported through relations with general child routines, family rituals, diabetes treatment adherence, and diabetes-specific family support. Completion of the PDRQ at the Baseline evaluation only will permit evaluation of the scale's predictive validity.

Measures obtained at Baseline, 6 months, and 12 months:

Parent self-efficacy (IPC): The Parental Self-Efficacy Scale for Diabetes Management (PSESDM)¹⁵³ was adapted from a prior measure for adult patients to measure parental self-efficacy for diabetes management of young children. The 8-item scale has adequate internal consistency ($\alpha=0.84$). Criterion validity was established. Higher scores were associated with more favorable HbA1c and quality of life in children.

Parent general psychological distress (IPC): The Brief Symptom Inventory-18 (BSI-18)¹⁵⁴⁻¹⁵⁵ is a widely used self-report screening measure that yields norm-referenced scores for Somatization, Depression, Anxiety and a Global Severity Index. Respondents rate their current status in terms of 18 physical and emotional complaints; on a scale from 0 (*not at all*) through 4 (*very much*). The BSI-18 has strong reliability and validity.¹⁵⁴⁻¹⁵⁵

Parent-Preschool Diabetes Adjustment Scale (PP-DAS): This is a 36-item measure constructed for this study in collaboration with our Parent Crowd and Family Advisors. The scale was designed as an effort to capture parents' status relative to the key domains of psychological adjustment revealed in our earlier qualitative study.

Benefit Finding Scale: This brief 16-item scale has been validated in several prior studies¹⁵⁶⁻¹⁵⁷ and will be used in this study to evaluate changes in parents' propensity to identify beneficial effects of their child's T1D on themselves, their children and their family relationships. Scale reliability has been consistently satisfactory to excellent in prior studies.

Parent fear of hypoglycemia (AC and BC): The 26-item Hypoglycemic Fear Survey – Parents of Young Children (HFS-PYC) measures parents' fear about their children's hypoglycemia.¹⁵⁸⁻¹⁶⁰ It yields two subscales, assessing parents' behaviors related to preventing hypoglycemia and their worry that their child may experience hypoglycemia. Parents rate how often each item is true for them on a 5-point Likert scale (1=never to 5=very often). The HFS-PYC has good internal consistency (α 's=0.86, 0.62, and 0.89) and test-retest reliability (r 's=0.91, 0.73, and 0.91) for the Total, Behavior, and Worry Scores, respectively.

Diabetes-specific child behavior problems (BC and ICC): The Preschool Diabetes Behavior Checklist (PDBC) was constructed for this study with extensive input from family advisors and the Parent Crowd. The scale measures the frequency of child behavior problems in children with T1D ages 2 to 6 years. The 32 items measure the child's behavior in the areas of general adjustment to T1D, glucose testing, dietary intake, and insulin delivery.

Diabetes Self-Management (DMB): The Diabetes Self Management Profile, Self-Report, Parent Form (DSMP-SR)¹⁶³ was derived from the previously validated DSMP structured interview. The 24-item scale quantifies treatment adherence. Mean + SD DSMP total scores (maximum possible = 84) were 54.7 + 12.6 for 145 parents. Internal consistency was α =0.80 and correlation with HbA1c was r =0.46.

Glycated Hemoglobin (HbA1c): For parents of children who receive T1D care at a Nemours facility, the child's most recent HbA1c, an index of average glycemia over the prior 2-3 months, will be obtained from the electronic medical record for the prior 12 months and for each T1D encounter occurring during the child's study enrollment. For participants enrolling online from non-Nemours centers, glycemic control will be measured via HbA1c collected using HemaSpot SE Blood Spot Collection Devices (dried blood spots [DBS]) obtained at 0, 6 and 12 months and analyzed at CoreMedica Laboratories in [name]'s Summit, MO. Correlations between DBS and standardized venous HbA1c are high and sensitivity and specificity for DBS for HbA1c are excellent^{165,166}. Higher values indicate higher average blood glucose over the prior 2-3 months.

Measures obtained at 6 months and 12 months only:

Website utilization: For each website user, we will track time-stamped logins and logouts, duration of login periods, hits on and duration of activity within specific website elements, etc. to provide careful tracking of extent and type of website use by each registered parent.

Qualitative interview: Parents will complete a qualitative interview at 3 months, 6 months and post-RCT, or earlier if the parent withdraws. The interview will obtain parents' perspectives of the website, suggested changes to content and design, advantages and disadvantages, reasons for low utilization, etc. We expect that this interview will yield relatively brief and focused responses from parents. Trained content analysts will employ a descriptive level of analysis, using a well-accepted method of content analysis via HyperRESEARCH software to extract the primary themes that emerge during these interviews. Analysts will be trained to a criterion of 90% inter-rater reliability. [name] will direct incorporation of these themes into the website.

Table 1. Measurement schedule for the randomized controlled trial phase of the proposed work.

Measure	Baseline	6 Months	12 Months
Demographic Information	•		
HbA1C	•	•	•

Family Management Measure: Parent Mutuality Scale	•		
Parenting Self-Efficacy Scale for Diabetes Management	•	•	•
Brief Symptom Inventory-18	•	•	•
Parent-Preschooler Diabetes Adjustment Scale	•	•	•
Benefit Finding Scale	•	•	•
Hypoglycemia Fear Survey-Parents of Young Children version	•	•	•
Preschool Diabetes Behavior Checklist-Revised	•	•	•
Eyberg Child Behavior Inventory	•		
Diabetes Self-Management Profile-Self Report Form	•	•	•
Pediatric Diabetes Routines Questionnaire	•		
Mid-RCT and Post-RCT Qualitative interview (Website group @ 3, 6 &12 months)	•	•	•

RCT Analytic Plans: The RCT analysis plan aligns with the focus of PA-DK-14-022, i.e., to develop an intervention that is ready for testing in a rigorous, multisite RCT. Because this is conceived as a preliminary RCT, we have put forth hypotheses below, but the plan emphasizes deriving effect size estimates for powering future trials on the main efficacy endpoints and analysis of website use and benefit. The planned RCT sample size of 150 families (2:1 for Website: UC) will suffice to estimate efficacy and to derive effect size estimates for use in a future trial with formal hypothesis testing.

Fundamentals: The Full Analysis Set will include parents who contribute data at either 6 or 12 mos.¹⁶⁷⁻¹⁶⁹ The Completer Analysis set will include those who provide data at 0, 6 and 12 mos..¹⁶⁷⁻¹⁶⁹ Efficacy analyses will be done on both sets.¹⁶⁷⁻¹⁶⁹ The statistician will make appropriate analytic adjustments for instances in which data are determined to be Missing at Random and Missing Completely at Random.¹⁶⁷⁻¹⁶⁹ In addition to multiple imputation, sensitivity analyses will be performed for assessing the robustness of the estimation in case of Missing Not At Random. Descriptive statistics will be calculated for all measures and distributions of obtained data will be summarized graphically in aggregate and by group. Assumptions for all proposed models will be checked before statistical analyses.¹⁶⁷⁻¹⁷¹ Appropriate transformations or non-parametric methods will be used in cases of violated model assumptions.¹⁶⁷⁻¹⁷¹ Sensitivity analyses will be conducted when assumptions underlying specific analyses cannot be verified using actual study data. Psychometric properties of all questionnaires will be calculated based on this sample's results, including internal consistency, 6 and 12-month test-retest reliability and predictive validity. All tests will be performed against a two-sided alternative at the $\alpha= 0.05$ significance level and a 95% confidence interval or a p-value will be provided for inferential purposes. All analyses will be performed using the most recent version of the SAS statistical software package.¹⁷² One way ANOVA of continuous baseline variables and a Fisher exact test/chi-square test/CMH test for categorical variables will be used to compare Website and UC at baseline.¹⁶⁷⁻¹⁷¹ Analyses of primary and secondary end points will be adjusted for imbalanced baseline characteristics.

Primary Analyses: Linear mixed effects modeling will be the primary analytic approach.¹⁷²⁻¹⁷⁷ Holmbeck's¹⁷⁸ methods will be used to evaluate moderation and mediation of treatment effects. Candidate moderators will include demographic variables and scores for each measure obtained at baseline. Candidate mediators will include scores on each questionnaire obtained at 0, 6 and 12 months. With three measurement points, these methods will be capable of detecting linear and quadratic longitudinal associations among study variables. We will test these primary hypotheses:

H1: Compared to UC participants, Website participants will have significantly more favorable status at 6 and 12 months on HbA1c (primary outcome) and secondary outcomes consisting of change in questionnaire scores at follow-up visits.

H2: Website treatment effects will be moderated by parental socioeconomic status and questionnaire scores at baseline visits

H3: Website treatment effects will be mediated by changes in change in questionnaire scores at follow-up visits.

H4: Among Website participants, the above treatment effects will be mediated by Website utilization (More utilization predictive of more beneficial effects).

Perhaps more importantly, this feasibility trial will yield rich data that will be used for estimation of effect sizes and sample size requirements for a future multi-center trial,¹⁷⁹⁻¹⁸⁰ and will enhance that application by:

1. Estimating Website-UC effect sizes (Cohen's *d* index)¹⁷⁹⁻¹⁸¹ at 6 and 12 months on the primary and secondary outcome variables.
2. Exploring utilization of the online resource, by examining demographic variables and individual characteristics of parents and children as moderators of Website use, and change in time-varying variables as mediators of change in Website use over 6 and 12 mo.¹⁷³⁻¹⁷⁸
3. Use of Structural Equation Modeling to evaluate and refine the conceptual model put forth earlier.¹⁸¹
4. Analyzing Mid-RCT and Post-RCT qualitative interviews of participants will provide additional information to drive refinements in the WEBSITE for future trials that could enhance WEBSITE use and benefit.

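### The Full Analysis Set is defined on parents, although families are randomised and HbA1c belongs to the child; the plan states neither one HbA1c record per child nor a family level for parent questionnaires

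*Combined protocol and SAP*

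**What the plan says.** All references are to the combined protocol and SAP.

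- **Enrolment** (4.2, Participants): "The RCT will enroll up to 300 parents of children <6 years old". One parent is enough, but "two parents of the same child will be encouraged to take part, in which case the mother and father will complete the measures separately". About 75 fathers are expected.
- **Randomised unit** (4.2, Study design): "each site will randomize families to Website and UC in a 2:1 ratio". The Human Subjects section also randomises families.
- **Primary outcome** (4.2, Study design and Glycated Hemoglobin): change in HbA1c over 6 months, measured on the child. The source is the medical record for Nemours patients ("For parents of children who receive T1D care at a Nemours facility, the child's most recent HbA1c") and a dried blood spot for the rest.
- **Analysis population** (4.2, RCT Analytic Plans, Fundamentals): "The Full Analysis Set will include parents who contribute data at either 6 or 12 mos". The Completer set requires data at 0, 6 and 12 months, with no unit named. Then: "Efficacy analyses will be done on both sets".
- **Inference** (same paragraph): two-sided tests at 0.05, and "a 95% confidence interval or a p-value will be provided for inferential purposes".
- **Model** (Primary Analyses): linear mixed effects modelling, with no random effects or levels listed.
- **Secondary outcomes** (H1): "secondary outcomes consisting of change in questionnaire scores at follow-up visits".
- **Counts**: RCT Analytic Plans gives 150 families. The Human Subjects section gives up to 300 families. Inclusion of Children projects 300 parents (225 mothers, 75 fathers) of 225 distinct children.

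**The concern.** Three units are in play. The family is randomised, the child supplies the primary outcome, and the parent defines the Full Analysis Set. They coincide only when each child has one enrolled parent. The protocol encourages two, and its own projection implies two for a third of the children (75 of 225).

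For HbA1c, two parents of one child bring one measurement between them. A dataset built on the parent-based set could hold that value twice, and nothing in the plan rules this out. If the two rows were treated as independent, the standard error would be too small and the 0.05 test too liberal. Any interval reported with the effect sizes, which are meant to size the next trial, would be too narrow. The HbA1c point estimate itself would shift only if the effect differed between one-parent and two-parent families.

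For the questionnaires, mother and father supply different scores, but both belong to the same randomised family. If their changes are correlated and the model has no family level, precision is again overstated, though by less.

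**Working it through.** **The plan's own figures.** The 150 families cannot be reproduced, because no effect size, SD, power or dropout is given. The enrolment counts do agree: 225 + 75 = 300 parents, and 28% of 300 = 84, the stated number of minority parents.

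**Two-parent children.** With at most two parents per child, 300 − 225 = 75 children have two. This assumes that no parent has two enrolled children.

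**HbA1c, conditional case.** Assume one row per parent, the child's value copied to each row, and rows treated as independent. Let w be the number of rows per child (1 or 2).

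- True variance divided by naive variance: R = Σw² / Σw
- Actual two-sided type I error: 2 × [1 − Φ(1.96 / √R)]

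| Scenario | R | √R | Type I error |
|---|---|---|---|
| No two-parent families | 225/225 = 1.000 | 1.000 | 0.050 |
| 225 children, 75 with two parents | (150 + 75×4)/300 = 1.500 | 1.225 | 0.110 |
| 225 children, half the fathers without follow-up data (assumed) | 337.5/262.5 = 1.286 | 1.134 | 0.084 |
| 150 families, 75 with two parents | (75 + 75×4)/225 = 1.667 | 1.291 | 0.129 |

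Simulated t-tests on change (2:1 allocation, no effect) agree. The 225/75 case gave 0.107 in 20,000 trials and 0.111 in a separate 40,000. The 150/75 case gave 0.129. One row per child gave 0.049 to 0.051. In the 225/75 case, coverage of a nominal 95% interval is about 1 − 0.11 = 89%.

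**On the Cohen's d scale** (SD 1, small effect, two-parent families spread 2:1, so 200 Website and 100 Usual Care rows):

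- Naive SE: √(1/200 + 1/100) = 0.122
- True SE of that same estimate: 0.122 × 1.225 = 0.150
- One row per child: √(1/150 + 1/75) = 0.141

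The duplicated analysis therefore reports more precision than it has, and is less precise than one row per child.

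**Does a family random intercept repair duplicated rows?** Take 225 children, 75 duplicated, three visits. The copied values add degrees of freedom but no information.

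- Expected within-family sum of squares: (150×2 + 75×4)σ² = 600σ²
- Nominal degrees of freedom: 150×2 + 75×5 = 675
- Residual variance is estimated at 600/675 = 0.889 of its true value
- R becomes 1.5/0.889 = 1.69, and type I error 0.131 (simulation 0.130)

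It does not.

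**Parent-reported change.** Let ρ be the mother-father correlation of change. R = 1 + 150ρ/(children + 75); with 225 children, R = 1 + 0.5ρ.

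| ρ (assumed) | R | Type I error | Simulation |
|---|---|---|---|
| 0 | 1.00 | 0.050 | 0.049 |
| 0.2 | 1.10 | 0.062 | 0.061 |
| 0.5 | 1.25 | 0.080 | 0.079 |

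The ρ = 0 simulation included a stable family level with correlation 0.5; it cancels out of change. The documents give no value of ρ. The inter-rater r of 0.44 quoted for the Parental Mutuality scale is a correlation of levels on a baseline-only measure, so it is not used.

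**The case against.** The strongest reply is that no harmful analysis is actually planned. The 11% needs three things together: a row per parent, the child's value copied to each row, and independence assumed. The documents state none of these for HbA1c, and several places lean the other way. The HbA1c paragraph speaks of the child's result, families are randomised, RCT Analytic Plans sizes the trial in families, and Inclusion of Children counts distinct children. A reader might infer that the plan will test HbA1c at an 11% error rate; the text does not support that.

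A reader might also infer that the mixed model has no random effects. They are unspecified, not absent. A mixed model can carry a family level, and the references cited for it include work on hierarchical and multilevel models.

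Nor is a parent-based set wrong in itself. Parents are the primary participants, and every scheduled outcome score other than HbA1c comes from a questionnaire that parents complete. Finally, this is described as a preliminary trial aimed at effect sizes, whose point estimates would be little affected.

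All of this limits the weight of the point without removing it. The family count is a sample size, not an analysis rule, and it sits just before a set defined on parents that is used for efficacy. Naming a mixed model does not settle the unit, since three visits need only a participant-level effect, and a family intercept on copied HbA1c rows does not help. The plan still sets tests at 0.05, and the precision of its effect sizes matters for planning the next trial.

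**Conclusion.** The point stands as a mismatch of units that should be resolved before analysis. The stated efficacy population does not match the randomised unit or the unit of the primary outcome, and no section reconciles them.

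For HbA1c, a literal parent-row analysis would give a type I error of about 11% on the projected 300 parents of 225 children, and about 13% with 150 families and 75 fathers. With no two-parent families there would be no inflation. These figures show what the gap permits; they are not forecasts of what will be done. They rest on copied values, assumed independence and the protocol's own enrolment projections, which differ between sections.

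For parent questionnaires the conclusion is weaker. Inflation is nil if mother and father changes are uncorrelated, and about 6% to 8% at assumed correlations of 0.2 to 0.5.

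**What to change.** Add to RCT Analytic Plans:

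1. **HbA1c.** Define the Full and Completer sets on randomised children (families). Use one HbA1c record per child per scheduled visit (0, 6 and 12 months), whether one or two parents enrol. Nemours records may hold a value for each encounter, so the scheduled visit has to be the unit. State that a family intercept on duplicated rows is not a substitute.
2. **Parent-reported outcomes.** Keep parents as records, with visits nested in parent and parents in family. Account for family through family-clustered standard errors or a family-by-visit effect. A parent-role term is optional.
3. **Reporting.** Compute the treatment tests, Cohen's d and all intervals from these models, and report the numbers of families, children and parents in each set.

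The cost is a few sentences, with no new data and no change to randomisation. The downside is slightly less favourable stated precision: on the projected counts, an SE of d of 0.141 where a parent-row analysis would show 0.122.
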